We will utilize single photon emission computed tomography (SPECT) methodology and gamma scintigraphy present in the GI laboratory of the outpatient Clinical Research Unit to study fasting gastric volumes and postprandial gastric accommodation responses and gastric emptying rates of a standardized meal in patients with functional dyspepsia and healthy subjects. Both groups will be studied twice, using crossover design, once with administration of secretin and once with placebo. This will provide each subject as his/her own control, as well as providing contrast in baseline and responsiveness to this hormone across the groups.

Rationale for Crossover design and selection of FD patients

The pathophysiology of functional dyspepsia includes:

- a. Delayed gastric emptying
- b. Accelerated gastric emptying (sometimes associated with impaired gastric accommodation)
- c. Reduced postprandial gastric accommodation
- d. Hypersensitivity to gastric mechanical distension
- e. Hypersensitivity to duodenal nutrients
- f. Duodenal inflammation
- g. Combinations of different mechanisms

Given the interest in secretin, we shall select patients with **FD and prior documentation of normal or accelerated gastric emptying and/or reduced gastric accommodation.** Given the diversity of mechanisms, the most efficient way to appraise the effects of secretin or PAM is through a crossover design.

Eligibility Criteria

Functional dyspepsia patients (n=15) and healthy subjects (n=15) aged 18-65 years will be recruited, and enrolled after providing written informed consent. The goal is to obtain the completed crossover results from 10 healthy and 10 Functional dyspepsia patients. Once that criterion is satisfied, enrollment will stop. The FD group will be identified from Mayo Clinic patients living within a 50 mile radius (Olmsted and Goodhue counties) who have symptoms consistent with this diagnosis and who have been studied and found to have normal or accelerated gastric emptying. Subjects may be involved in study activity for up to six weeks from screening date to completion of all studies. The actual study will be conducted on two separate days, each involving 3-4 hours of study. These testing visits should be scheduled one week apart, but within 4 weeks.

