Male and female subjects, aged 18 to 65 years at screening, who meet the following criteria, will be eligible for enrollment. A detailed history will be obtained with validated questionnaires [including Hospital Anxiety and Depression Inventory, Functional Dyspepsia Symptom Diary, abridged Bowel Disease questionnaire (for healthy subjects only) and the long Bowel Disease (for functional dyspepsia patients only) (Zigmond & Snaith 1983, Patient-Reported Outcome Consortium's Functional Dyspepsia Working Group 2018, Talley 1990, Talley 1990)].

Inclusion criteria:

- Able to provide written informed consent prior to any study procedures and be willing and able to comply with study procedures
- No medical problems or chronic diseases that could significantly affect GI function, other than functional dyspepsia, for that group
- Body mass index of 18-40 kg/m²

- Female subjects must have negative urine pregnancy tests and must not be lactating prior to receiving study medication and radiation exposure. For females able to bear children, a hormonal (i.e., oral, implantable, or injectable) and single-barrier method, or a double-barrier method of birth control must be used throughout the study. Female subjects unable to bear children must have this documented in the medical record [i.e., tubal ligation, hysterectomy, or post-menopausal (defined as a minimum of one year since the last menstrual period)].
- Rapid or normal gastric emptying (GE) measured via scintigraphy in past 5 years for FD subjects
- Normal upper endoscopy (EGD) in past 5 years for FD subjects

Exclusion criteria:

- Significant change in symptoms since previous EGD and/or GE study for FD subjects
- Unable or unwilling to provide informed consent or to comply with study procedures
- Structural or metabolic diseases that affect the GI system
- Unable to stop acid reducers such as proton pump inhibitors, H2 blockers 3 days prior to study days
 - o May permit antacids on as needed basis but must stop 8 hours before study days
- Unable to avoid the following over-the-counter medications 48 hours prior to the baseline period and throughout the study:

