(including performance characteristics) in our lab. Using the ratio of postprandial volume over the fasting volume is a measure of the postprandial gastric accommodation. Radiation exposure listed in Appendix.

Gastric Emptying

To assess gastric emptying during the satiation test (10), the first 300 mL of Ensure® will be radiolabeled with 50

[figure not shown]
μCi of ¹¹¹In-DTPA and 2-minute duration anterior and posterior scans of the abdomen will be obtained right after the Ensure is ingested and then 15 minutes (which will be after the end of SPECT imaging) at 5 minute intervals and then through 30 minutes from first 300mL of Ensure®. Radiation exposure listed in Appendix.

Plasma Measurements Blood draws (18 cc each) will be taken during fasting (in two occasions) and postprandially (at 15, 45 and 90 minutes after starting ingestion of Ensure) during the gastric function measurements. We will measure plasma levels of GIP, pancreatic polypeptide, and glucagon-like peptide-1 (GLP-1). A blood sample for possible future DNA testing will be collected also.

GLP-1 will be measured as the biologically active GLP-1 (active and total) using a 2-site, non-competitive immunoassay based on enzyme-labeled quantification of GLP-1 detected by a fluorogenic substrate. Total **GIP** will be measured using a two-site sandwich immunoassay using a total GIP ELISA kit (Millipore Corp, Billerica, MA, USA); the antibody used specifically recognizes human GIP (1-42) and GIP (3-42), but not other forms of oxyntomodulin, GLP-1, or GLP-2. Pancreatic polypeptide will be measured (at Mayo ICL) on the same plasma samples using radioimmunoassay technique.

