Sample size assessment for primary aim to examine the *within* dyspepsia patient response when receiving Secretin versus Placebo. Sample size is based on the results of primary endpoints in the Mayo Clinic lab [data show mean \pm SD). Within 10 dyspepsia patients, assuming a two-sided paired T test (80% power, α =0.05) in this crossover trial demonstrable differences for secretin compared to placebo is **21% in fasting gastric volume**, **13.0% in**

postprandial gastric volume and 16.6% in amount of gastric retention of Ensure at 30 minutes based on the coefficients of variation observed from the Mayo Clinic laboratory of Dr. [name] in prior studies as shown in the table below.

Response	Mean	SD	Effect size detectable (absolute [% of mean], n=10 Based on cross-over design		
Fasting gastric volume, mL Post prandial gastric volume, mL	273 848	57 111	56.8mL (20.8%) 110.6mL (13.0%)		
Gastric emptying expressed as retention of Ensure at 30 mins, (%)	72	12	11.95 (16.6%)		
Volume to fullness, mL	755	330	328.5mL (43.5%)		
Maximum tolerated volume, mL	1283	400	398.5mL (31.1%)		
Peak postprandial GLP-1, pmol/L	18.8	14	13.94pmol/L (74.1%)		

Therefore the study is powered to detect clinically relevant effects of the study medication.

A similar analysis will be conducted in the healthy human volunteers based on the cross-over design, and the anticipated effect sizes that would be demonstrable in this second group is similar to that summarized above for patients with functional dyspepsia.

A subsidiary (secondary) analysis will compare the response using secretin in FD and healthy volunteers. This will be a 2 sample, unpaired analysis of the observations on secretin treatment, with ten patients in each cohort.

The table below shows the effects sizes demonstrable for the comparison between FD and health, using a 2-group analysis (unpaired analysis), again a two-sided test at α =0.05, with 80% power.

Response	Mean	SD	Effect size detectable (absolute [% of mean], n=10 Based on 2-group comparison
Fasting gastric volume, mL Post prandial gastric volume, mL	273 848	57 111	75.5mL (27.7%) 147.0mL (17.3%)
Gastric emptying expressed as retention of Ensure at 30 mins, (%)	72	12	15.9 (22.1%)
Volume to fullness, mL	755	330	437mL (57.9%)
Maximum tolerated volume, mL	1283	400	530mL (41.3%)

Peak postprandial GLP-1, pmol/L	18.8	14	18.55pmol/L (98.8%)
---------------------------------	------	----	---------------------

Statistical Methods

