It is anticipated that all primary and secondary endpoints will be normally distributed. We will use parametric tests to assess study parameters. If the data are not normally distributed we will use non-parametric tests.

For the primary aim, comparison of responses in the 10 completed dyspepsia patients for secretin versus placebo, as well as the subsidiary, analogous study conducted in healthy volunteers, the analysis will be a paired test, either a paired t test or signed rank test.

For the secondary aim, comparison of 10-15 dyspepsia patients with 10-15 healthy controls for responses after receiving secretin, the analysis will be either a two-sample t test or a rank sum test.

Covariate analysis may be conducted using a regression model, including gender and BMI as covariates, since these may significantly affect gastric functions such as satiation maximum tolerated volume, and smoking and gender since this may significantly affect drug levels of secretin. It is unclear if these covariate analyses will be required given the small sample sizes (n=10 in each group)

Safety Considerations

Informed consent

A complete description of the study will be presented to each potential study participant and signed and dated informed consent will be obtained before any study specific procedures are performed.

Demographics and medical history

A medical history and review of body systems along with demographic data will be obtained for all patients during the screening period (Days -30 to -1). Data that will be recorded in the source document/CRF include gender, race, date of birth, cigarette smoking history, alcohol use, drug abuse history and concomitant medication use.

Physical examination

A physical examination will be performed during the screening period to confirm eligibility.

Concomitant medication review

A review of concomitant medications will be conducted during the screening period and at every study visit. Any medications taken by study patients or changes in dose regimens will be recorded on a Concomitant Medication CRF.

Vital signs and weight

Vital signs will be obtained in the sitting position. Body temperature (°C), respiration rate (breaths/minute) and weight will be recorded at each time point when vital signs are measured. Height (cm) will be measured at the screening visit.

Pregnancy testing

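### Nothing balances or firmly adjusts the secondary FD-versus-health comparison for sex and BMI, two factors the plan itself thinks may influence its endpoints

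*Combined protocol and SAP*

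**What the plan says.** - **Covariates.** Statistical Methods says a regression may be run, "including gender and BMI as covariates, since these may significantly affect gastric functions such as satiation maximum tolerated volume". Smoking and gender are added because they might alter secretin levels. The section then leaves the matter open: "It is unclear if these covariate analyses will be required given the small sample sizes (n=10 in each group". It names no response variable, no trigger and no test to which the regression belongs.
- **FD versus health.** Sample Size Determination calls this a subsidiary (secondary) analysis: an unpaired comparison of values on secretin, "again a two-sided test at α =0.05, with 80% power". Statistical Methods gives a two-sample t or rank-sum test, with no covariates.
- **Within group.** The secretin-saline comparison is a paired t or signed-rank test, also without covariates. Study Design says of the crossover: "This will provide each subject as his/her own control".
- **Who enters.** Both groups admit men and women aged 18 to 65, with "Body mass index of 18-40 kg/m²". FD patients are identified among local clinic patients; the source of the healthy volunteers is not stated. The target is fixed: "The goal is to obtain the completed crossover results from 10 healthy and 10 Functional dyspepsia patients".
- **Randomization.** Under Experimental Procedures, it assigns treatment order within each group. It cannot balance FD against health.

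**The concern.** FD status is not randomized, so any factor that affects an endpoint and is distributed differently in the two groups can appear as an FD effect. The plan names two candidates, and the reference it cites for the nutrient drink test mentions sex, BMI and age in its title. It neither balances them at recruitment nor commits to adjusting for them. The reason given for doubting the adjustment, small samples, is also what makes a chance imbalance likely.

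Two results are at stake: the Aim 3 comparison, and the contrast in baseline between groups that Study Design promises. Because the Aim 3 test uses secretin-day values and not secretin-minus-placebo differences, the additive part of any sex or BMI effect enters it in full.

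**Working it through.** **Inputs from the protocol.** n = 10 completers per group; two-sided alpha 0.05; 80% power; MTV SD 400 mL; detectable differences for MTV of 398.5 mL (paired) and 530 mL (two-group).

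**Assumed inputs.** The protocol gives no sex mix and no sex effect. Assumed here: 80% women in FD, 50% in health; sex effect on MTV of 200 to 400 mL (0.5 to 1.0 SD).

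**1. The plan's own figures.** With noncentral t power:
- Paired, 9 df: detectable 0.996 SD; 0.996 × 400 = 398.4 mL (stated 398.5).
- Two-sample, 18 df: detectable 1.325 SD; 1.325 × 400 = 530 mL (stated 530).

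The other five rows of both tables also reproduce, so the sample-size arithmetic is sound. Neither table makes any allowance for sex or BMI.

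**2. Spurious group difference.** Bias = difference in proportion of women × sex effect.
- (0.8 − 0.5) × 200 mL = 60 mL = 0.15 SD
- (0.8 − 0.5) × 400 mL = 120 mL = 0.30 SD

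**3. False-positive rate with no true FD effect.** Two-sample t, noncentrality = shift in SD × √(n/2), 18 df, critical value 2.101:
- 0.15 × √5 = 0.335, rejection rate 6.2%
- 0.30 × √5 = 0.671, rejection rate 9.7%

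This takes 400 mL as the whole within-group SD. Simulations that instead took 400 mL as the SD within each sex, with fixed numbers of women, gave:

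| Women, FD v health | Sex effect | Bias | Type I error, unadjusted |
|---|---|---|---|
| 8/10 v 4/10 | 200 mL | about 80 mL | 6.4% |
| 8/10 v 4/10 | 400 mL | about 160 mL | 9.6% |
| 8/10 v 2/10 | 200 mL | about 120 mL | 9.0% |
| 8/10 v 2/10 | 400 mL | about 240 mL | 19.8% |

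On that second reading a given bias inflates the error less, because the sex effect also widens the estimated SD. Adjusting for sex brought all four cases back to about 5%.

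**4. Chance imbalance.** For two independent Binomial(10, 0.6) counts, P(difference of three or more women) = 0.253. With 50% women in each group, the probability is 26% for three or more and 12% for four or more.

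**5. The paired tests.** Simulated with n = 10, true effect 398.5 mL, five women and five men:
- An additive sex effect of 400 mL leaves power at 80%; it cancels within person.
- If the secretin effect itself differs by sex by 400 or 800 mL, paired t power is about 71% or 48%. Regressing the within-person difference on centred sex gives about 79% in both cases.
- If sex does not modify the effect, that regression costs one or two percentage points of power.

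**The case against.** The strongest reply is that the harm is assumed, modest and confined to a secondary analysis. All sex and BMI inputs are assumptions; 60 to 120 mL is only 11% to 23% of the 530 mL the comparison can detect (60/530, 120/530); and the primary FD crossover result is untouched. All of that stands, and it limits the weight of the point. It does not remove it: group composition cannot be changed after enrollment, and 20 people leave little room to separate the factors afterwards.

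A second reply is that comparing secretin-minus-placebo differences between groups would remove additive sex and BMI effects without any matching. That is correct and worth considering. It would not protect the baseline contrast, nor a response to secretin that sex modifies, which the plan's remark about gender and secretin levels makes possible.

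A third is practical: matching to enrolled patients does not guarantee balance among completers, and fine BMI bands by sex would give too many cells for 10 people. This is why the split should be coarse.

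Three stronger readings might be inferred, and the documents support none of them:
- **Covariates are useless in the paired tests, or should be deleted from them.** Only additive effects cancel, as step 5 shows, and the planned paired tests contain no covariates to delete.
- **The smoking rationale is invalid because secretin is not assayed.** Plasma Measurements says "We will measure plasma levels of GIP, pancreatic polypeptide, and glucagon-like peptide-1 (GLP-1" and lists no secretin assay. But a suspected modifier of exposure can be a reasonable covariate precisely when exposure is unmeasured, and smoking history is recorded.
- **The plan asserts that sex and BMI do affect its endpoints.** It says only that they may.

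**Conclusion.** The point holds for the secondary FD-versus-health comparison. As written, the plan leaves it open to confounding by two factors the plan itself names, and its only remedy is an optional regression with no trigger and no link to that test. Under the stated assumptions the bias is 60 to 120 mL of MTV and the type I error 6.2% to 9.7%; a more extreme sex mix gives more, a milder one little. No comparable figure was derived for BMI, although the reasoning is the same. The chance-imbalance figure of 25% needs only the assumption of 60% women in both groups.

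The within-group secretin-saline tests, including the primary aim, are not confounded by sex or BMI and need no change. The amendment is worth making because it is cheap, but the primary conclusion does not depend on it.

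**What to change.** 1. **Eligibility Criteria.** Recruit healthy volunteers frequency-matched to the FD patients on sex and one coarse BMI split (for example below 30 versus 30 or above), which makes four cells. Update the targets as FD patients complete, so that the balance applies to the completers.
2. **Statistical Methods.** Replace the open-ended covariate paragraph, as far as it concerns FD versus health, with one pre-specified sensitivity analysis: a linear model with group, sex and BMI, reported beside the unadjusted test whatever the observed imbalance.
3. **Within-group tests.** Leave the paired tests as they are. Label any regression of the within-person difference on centred sex or BMI as exploratory.

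The cost is a recruitment instruction covering at most 15 volunteers, with slightly slower healthy enrollment because it must follow the FD group. In the sensitivity analysis two degrees of freedom are lost (20 − 2 = 18 becomes 20 − 4 = 16). Sex, weight and height are already recorded, so no new measurement is needed.

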- 11. Chial HJ, [name] C, Delgado-Aros S, [name] D, Thomforde G, Ferber I, [name] M: A nutrient drink test to assess maximum tolerated volume and postprandial symptoms:

effects of gender, body mass index and age in health. Neurogastroenterol Mot 14:249-253, 2002

Appendix

Satiation test: Levels of Fullness Questionnaire

Nutrient Drink Test

	Protocol: IRB#		
Namei _{ss}		Clinie#	Date
	Start Time:		
	Satiety (Level of Fullness)		
	First Sensation (1):		-
	Mild Satiety (2):		-
	Please notify staff w	hen you have reached	this level
	Moderate Satiety (3):		
	Severe Satiety (4):		-
	Maximum Satiety (5):		_Stop Time.
	Please re	turn form to GI Lab.	
		Staff Use Only.	
		Total# of cans	
		Total Volume Consum	ed:
		Time	

Satiation test: VAS Symptom Scales

Nutrient Drink Test

Protocol: IRB# _____

Please return form to GI Lab

Please indicate below your level of nausea:

Worst Ever

Please indicate below your level of fullness:

None	Worst Ever

Please indicate below your level of bloating:

None	Wo	rst Eve

Please indicate below your level of abdominal pain:

Gastric Accommodation and Gastric Emptying tests: Radiation Exposure

SPECT (upper table) and Gastric Emptying (lower table)

Investigator:	[name] [name]			-							RSC Nu	mber:						
Model: Adult								Organ	n/₩t (o	raan o	loses :	are in m	Gv)						
	O a bissibus and	Activity per	Number of				DDM									01 0		-	
RAM	Activity per administratio n (mCi)	administratio n (MBq)	administration s	Testes 0.1	Ovaries 0.1	0.05	0.12	0.12	0.05		0.12	O.12		0.05		0.025	Remaind 0.025	er]	
To-99m Non- Absorbable Markers (liquid,	10	370	2	0.96	10.24		3.70					43.66				45 14	200		
In-111 Non- Absorbable Markers	10	310	2	0.36	13.24	0.33	3.10	0.74								45.14	2.69		
(liquid, oral)	0.1	3.7	2	0.22	3.11	0.03	0.72	0.04	0.00	0.23	11.32	0.89	0.89	0.25		3.70]	
Total Effective Dose				0.12	22.35	0.42	0.53	0.78	0.03		85.32 10.24	5.35	0.30	3.43 0.17	0.25	1.22	2.98 0.07	E (mSv):	20.40
				Remainder organ	adrenal	brain	kidney	muscla	pancrea	. SI	snleen	thymus	uterus	\ _e /eigh	ated.				
			i c-aam Non- Absorbable	Mass (g)	14	1420	310	28000	100	640	180	20	80	Avera					
				Organ dos	2.66	0.00	4.88	2.74	8.14		5.40	0.25	11.84	2.69					
			In-111 Non- Absorbable Markers (liguid, oral)	Organ dos	0.15		0.31	0.31	0.33		0.24		1.26	0.29			0		
												•	Subj	ect	Init	ials:			

Questionnaire: Hospital anxiety and depression questionnaire (Zigmond & Snaith 1983)

Screen Number: _____

Please read each item and circle the reply which best describes how you have been feeling during the past week. Don't devote too much time to your responses; your immediate reaction will probably be more accurate than a long thought out response.

1. I feel tense or 'wound up':

Most of the time A lot of the time Occasionally Not at all

2. I still enjoy the things I used to enjoy:

Definitely as much Not quite so much Only a little Hardly at all

3. I get a frightened feeling, as if something awful is about to happen:

Very definitely and quite badly Yes, but not too badly A little, but it doesn't worry me Not at all

4. I can laugh and see the funny side of things:

As much as I always could Not quite so much now Definitely not so much now Not at all

5. Worrying thoughts go through my mind:

A great deal of the time A lot of the time From time to time Only occasionally

6. I feel cheerful:

Not at all Not often Sometimes Most of the time

7. I can sit at ease and feel relaxed:

Definitely Usually Not often Not at all

8. I feel as if I am slowed down:

Nearly all the time Very often

	Sometimes Not at all	
9.	I get a frightened feeling, like 'butterflies in the stomach':	
	Not at all Occasionally Quite often Very often	
10.	I have lost interest in my appearance :	
	Definitely I don't take as much care as I should I may not take quite as much care I take just as much care as ever	
11.	I feel restless as if I have to be on the move :	
	Very much indeed Quite a lot Not very much Not at all	
12.	. I look forward with enjoyment to things :	
	As much as I ever did Rather less than I used to Definitely less than I used to Hardly at all	
13.	. I get sudden feelings of panic :	
	Very often indeed Quite often Not very often Not at all	
14.	. I can enjoy a good book or TV program :	
	Often Sometimes Not often Very seldom	
Sig	gn Date	

Questionnaire: Functional Dyspepsia Symptom Diary (Patient-Reported Outcome Consortium's Functional Dyspepsia Working Group 2018)

Subject Initials:	
Screen Number:	

Functional Dyspepsia Symptom Diary (Am J Gastroenterol. 2018; 113: 39–48)

FDSD Item	0=No; 10=Worst imaginable										
	0	1	2	3	4	5	6	7	8	9	10
1. Stomach pain.											
2. Burning in the stomach.											
3. Nausea											
4. Bloating											
5. Stomach fullness											
6. Early satiety											
7. Burping/belching rating											
8. Burping/belching bother											

Questionnaire: Abridged bowel disease questionnaire (Talley, 1990) (healthy subjects only):

Subjects Initials	
Screen Number	

In the past 12 months, have you experienced the following?

QUESTION	YES	NO
1. 2 or less than 2 bowel movements/week		
2. Excessive straining or sensation of incomplete evacuation of stool on more than 25% of occasions		
3. Lumpy stools on more than 25% of occasions		
At least 3 months of continuous or recurrent symptoms of:		
4. Abdominal pain or discomfort relieved by defecation		
5. Abdominal pain or discomfort associated with a change in stool frequency		
6. Abdominal pain or discomfort associated with a change in stool consistency		
7. More than 3 bowel movements per day		
8. Loose watery stools		
9. Bloating		
10. Swallowing difficulties		
11. Upper abdominal pain after meals more than once a month		
12. Abdominal bloating after meals		
13. Nausea regularly more than once a month		
14. Vomiting regularly more than once a month		
15. Heartburn regularly more than once a week		
16. Acid reflux regularly more than once a week		

Sign	Date

Questionnaire: Long bowel disease question patients only)	inaire (Talley 1990) (functional dyspepsia
	Subject Initials:
	Screen Number

A QUESTIONNAIRE OF GASTROINTESTINAL SYMPTOMS

Please answer ALL questions. If you are uncertain, please write down your best guess. It is easy to miss questions, so *please check that you haven't left any out as you go.* If you wish to comment on any questions or qualify your answers, use the space in the margins; these comments will be read and taken into account.

All information provided will be kept confidential.

Thank you for your help.

First we would like to ask you some questions about TROUBLE SWALLOWING (a feeling that food sticks in your throat or chest) in the last year.

1.	Have you	had difficulty swallowing in the last year ? (Check one)
$1 \square \text{No} \rightarrow$		Please go to question 9 on PAGE 2.
2 [□ Yes →	Please answer the following questions.
		\downarrow
2.		your life did this trouble swallowing FIRST begin, as close as you can recall?
	(Check o	,
		ast 6 months
		hs to 1 year ago nan 1 year to 2 years ago
		nan 2 years to 5 years ago
		nan 5 years to 10 years ago
	6 □ More tl	nan 10 years to 20 years ago
	7 ☐ More tl	nan 20 years ago
3.	How ma	ny times have you had this trouble swallowing in the last year? (Check one)
	1 ☐ Less th	an once a month
		once a month
		once a week
	4 □ Several 5 □ Daily	times a week
	J 🗆 Dany	
4.	How bad	is your trouble swallowing usually? (Check one)
	1 🗆 MILD	- can be ignored if I don't think about it
		RATE - cannot be ignored, but does not affect my life-style
		RE - affects my life-style
	4 □ VERY	SEVERE - markedly affects my life-style
5.	Does it h	urt (is it painful) when you swallow? (Check one)
	1 □ No	
	2 □ Yes	

6.	•		
7.	1 □ Yes, ra 2 □ Yes, sl	retrouble swallowing gotten progressively worse in the last year? (Check one) rapidly worse slowly worse as not gotten worse	
8.	-	our trouble swallowing come and go so that there are times when you have no troub fer what you eat? (Check one)	ole
Next, we	would like to	to ask you some questions about heartburn in the last year .	
9. yea	•	had a burning pain or discomfort behind the breast bone in your chest in the lad NOT count pain in your stomach or pain from heart trouble.) (Check one)	ıst
1 [□ No →	Please go to question 16 on PAGE 3.	
2 [□ Yes →	Please answer the following questions.	
the breas		tm "heartburn" will be used to mean a burning pain or discomfort behind our chest. When answering these questions, please do not count any other burn".	
10.	1 □ In the 2 □ 7 mon 3 □ More t 4 □ More t 5 □ More t 6 □ More t	n your life did this heartburn FIRST begin, as close as you can recall? (Check one) last 6 months on this to 1 year ago than 1 year to 2 years ago than 2 years to 5 years ago than 5 years to 10 years ago than 10 years to 20 years ago than 20 years ago	

11.	How many times have you had heartburn in the last year? (Check one) 1 □ Less than once a month 2 □ About once a month 3 □ About once a week 4 □ Several times a week 5 □ Daily
12.	How bad is your heartburn usually? (Check one) 1 □ MILD - can be ignored if I don't think about it 2 □ MODERATE - cannot be ignored, but does not affect my life-style 3 □ SEVERE - affects my life-style 4 □ VERY SEVERE - markedly affects my life-style
13.	Has your heartburn awakened you at night in the last year? (Check one) $1 \square \text{No}$ $2 \square \text{Yes}$
NO	TE: When we say "often" we mean more than 25% of the time in the last year.
14.	Does your heartburn often travel up toward your neck ? (Check one) 1 □ No 2 □ Yes
15.	Is your heartburn often made better (eased) by taking antacids (like Amphojel, AlternaGEL, Gaviscon, Maalox, Mylanta, Riopan, Rolaids or Tums)? (Check one) 1 □ No 2 □ Yes 3 □ I have not taken antacids for heartburn
We would	I now like to ask you about other complaints you have had in the last year .
16. yea	How many times have you had a feeling of WANTING TO THROW UP (nausea) in the last r? (Check one)
2	None □ Less than once a month
	B □ About once a month I □ About once a week
_	5 □ Several times a week 6 □ Daily
	Please check that all questions that apply to you have been answered.

17.	How many times have you ACTUALLY THROWN UP (vomited) in the last year? (Check one) 1 □ None 2 □ Less than once a month 3 □ About once a month 4 □ About once a week 5 □ Several times a week 6 □ Daily
18.	Have you thrown up (vomited) bright red blood in the last year? (Check one) 1 □ No 2 □ Yes
19.	Has your food come back up into your mouth or throat in the last year? (Please do not include vomiting) (Check one) 1 □ No 2 □ Yes
	NOTE: When we say "often" we mean more than 25% of the time in the last year.
20.	Have you often been troubled by burping (belching) up gas through the mouth in the last year? (Check one) 1 □ No 2 □ Yes
21.	Have you often been troubled by hiccups in the last year? (Check one) 1 □ No 2 □ Yes
22.	Have you lost weight in the last year without deliberately dieting? (Check one) 1 □ No 2 □ Less than 7 lbs. 3 □ 7 lbs. or more
23.	Is your appetite in the last year compared with before: (Check one) 1 □ Decreased? 2 □ About the same? 3 □ Increased?
	Please check that all questions that apply to you have been answered.

24. Have you often lost your appetite and felt full soon after starting to eat so that you could not finish a normal meal in the last year? (Check one) 1 □ No 2 □ Yes
Next, we would like to ask you some questions about stomach, belly or tummy pain in the last year.
25. Have you had an ache or pain in your stomach or belly (gut) in the last year? (Please do NOT coun cramps or pain with menstrual periods, heartburn, or chest pain.) (Check one)
$1 \square \text{No} \rightarrow $ Please go to question 45 on PAGE 8.
2 □ Yes → Please answer the following questions.
↓
Stomach or belly pain can be difficult to describe and sometimes more than one type of pain can occur. Please think about the usual or primary type of pain you have. We would like to ask you some questions only about the USUAL or PRIMARY pain in your stomach or belly.
26. Have you had this same ache or pain more than SIX times in the last year? (Check one) 1 □ No 2 □ Yes
 27. How bad is the ache or pain usually? (Check one) 1 □ MILD - can be ignored if I don't think about it 2 □ MODERATE - cannot be ignored, but does not affect my life-style 3 □ SEVERE - affects my life-style 4 □ VERY SEVERE - markedly affects my life-style
 Does the usual ache or pain EVER WAKE YOU FROM SLEEP AT NIGHT? (Check one) 1 □ No 2 □ Yes
 Does this pain come and go periodically? (Periodically here means periods of at least a month with no pain, with periods in between of weeks to months when there is pain.) (Check one) 1 □ No 2 □ Yes
Please check that all questions that apply to you have been answered.

30.	How many times did you get this pain in the last year? (Check one) 1 □ Less than once a month 2 □ About once a month 3 □ About once a week 4 □ Several times a week 5 □ Daily
31.	When this pain occurs, how long does it usually last? (Check one) 1 □ Less than 30 minutes 2 □ 30 minutes to 2 hours 3 □ More than 2 hours to 6 hours 4 □ More than 6 hours
32.	When in your life did this ache or pain FIRST begin as close as you can recall? (Check one) 1 □ In the last 6 months 2 □ 7 months to 1 year ago 3 □ More than 1 year to 2 years ago 4 □ More than 2 years to 5 years ago 5 □ More than 5 years to 10 years ago 6 □ More than 10 years to 20 years ago 7 □ More than 20 years ago
33.	Does this ache or pain often occur BEFORE meals or when hungry? (Check one) 1 □ No 2 □ Yes
NOT	E: When we say "often" we mean more than 25% of the time in the last year .
34.	Does this ache or pain often occur IMMEDIATELY AFTER (less than 30 minutes meals? (Check one) 1 □ No 2 □ Yes
35.	Does this ache or pain often occur 30 minutes to 2 hours AFTER meals? (Check one) 1 \square No 2 \square Yes
36.	Is this pain often made BETTER (relieved) by burping (bringing up air through the mouth)? (Check one) 1 □ No 2 □ Yes
	Please check that all questions that apply to you have been answered.

37.]	Is this pain often made BETTER by having a bowel movement? (Check one) 1 □ No 2 □ Yes
38.	Is this pain often made BETTER by eating? (Check one) 1 □ No 2 □ Yes
39.	Is this pain often made BETTER by taking antacids (like Tums, Riopan, Mylanta, Maalox, Gaviscon or Rolaids)? (Check one) 1 □ No 2 □ Yes 3 □ I don't take antacids
40.	Is this pain often made WORSE by food or milk? (Check one) 1 □ No 2 □ Yes
41.	Do you often have MORE bowel movements when this pain begins? (Check one) $1 \square No$ $2 \square Yes$
42.	Do you often have LOOSER bowel movements (stools) when this pain begins? (Check one) 1 □ No 2 □ Yes
43.	Do you often feel bloated and actually see your belly swell up? (Check one) $1 \square No$ $2 \square Yes$
44.	Have you seen MUCUS in your stools in the last year (that is, white or green slimy material)? (Check one) 1 □ No 2 □ Yes

	n important purpose of this study is to learn about bowel habits in the community the last year.
45.	In the last year, how regular were your bowel movements? (Check one)
	 1 □ Often had constipation (more than 25% of the time) 2 □ Sometimes had constipation (less than 25% of the time) 3 □ Alternating diarrhea and constipation 4 □ Sometimes diarrhea (less than 25% of the time) 5 □ Often had diarrhea (more than 25% of the time) 6 □ Usually normal
46.	What is the longest number of days you have ever gone without having a bowel movement in the last year? (Check one)
	1 □ 2 days or less 2 □ More than 2 to 4 days 3 □ More than 4 days to 1 week 4 □ More than 1 to 2 weeks 5 □ More than 2 weeks
47.	How many bowel movements do you usually have in a WEEK? (Check one)
	1 □ 1 or less 2 □ 2 3 □ 3-4 4 □ 5-8 5 □ 9-12 6 □ 13-16 7 □ 17-21 8 □ 22-26 9 □ More than 26
48.	In the last year, did you need to take anything to help you have a bowel movement (such as laxative, enema, or suppository, but not including fiber products)? (Check one)
	 1 □ No 2 □ Yes, sometimes (less than 25% of the time) 3 □ Yes, often (more than 25% of the time) 4 □ Yes, usually (more than 75% of the time)
	If yes, what did you take?

mov	In the last year, have you needed to strain a lot (for more than 1 to 2 minutes) to have a bowel ement? (Check one)
	 1 □ No 2 □ Yes, sometimes (less than 25% of the time) 3 □ Yes, often (more than 25% of the time) 4 □ Yes, usually (more than 75% of the time)
	How severe was your straining with bowel movements in the last year? (Check one) 1 □ I never strain with bowel movements 2 □ Very mild 3 □ Mild 4 □ Moderate 5 □ Severe 6 □ Very severe
,	In the last year, have your stools been loose or watery? (Check one) 1 □ Never 2 □ Sometimes (less than 25% of the time) 3 □ Often (more than 25% of the time) 4 □ Usually (more than 75% of the time)
,	In the last year, have your stools been hard? (Check one) 1 □ Never 2 □ Sometimes (less than 25% of the time) 3 □ Often (more than 25% of the time) 4 □ Usually (more than 75% of the time)
	In the last year, after finishing a bowel movement, have you felt there was still stool that needs to be passed? (Check one) 1 □ No 2 □ Yes
	In the last year, have you experienced an urgent need to open your bowels that made you rush to the toilet? (Check one) 1 □ Never 2 □ Sometimes (less than 25% of the time) 3 □ Often (more than 25% of the time) 4 □ Usually (more than 75% of the time)
	Have you noticed ANY BLOOD in your stools or in the toilet bowl in the last year? (Check one) 1 □ No 2 □ Yes
	Please check that all questions that apply to you have been answered.

	In the last year, did you ever press your finger in or around the anus (back passage) to help a vel movement come out? (Check one)
	1 □ No 2 □ Yes
57.	How much time did you usually need to spend each time on the toilet to move your bowels during the last year? (Check one)
	1 □ Less than 5 minutes 2 □ 5 to 10 minutes 3 □ More than 10 minutes up to 30 minutes 4 □ More than 30 minutes up to 1 hour 5 □ More than 1 hour
58.	In the last year, did you have to position yourself other than in the sitting position to help a bowel movement come out? (Check one)
	 1 □ Never 2 □ Sometimes (less than 25% of the time) 3 □ Often (more than 25% of the time) 4 □ Usually (more than 75% of the time)
	If yes, which position usually?
59.	In the last year, did you feel there was a blockage in your rectum or anus (back passage) which made it difficult for you to pass the stool? (Check one)
	1 □ Never 2 □ Sometimes (less than 25% of the time) 3 □ Often (more than 25% of the time) 4 □ Usually (more than 75% of the time)

	No →	Please go to question 70 on PAGE 13.
		3 7
	Yes →	Please answer the following questions.
		\downarrow
61.	AD, etc. 1 □ No 2 □ Yes, s 3 □ Yes, o 4 □ Yes, t	ast year, did you have to take medication (like antidiarrheals, Lomotil, Imodium) to prevent leakage of stool? (Check one) sometimes (less than 25% of the time) often (more than 25% of the time) asually (more than 75% of the time)
